## Manual of Procedures for the Institutional Amyloidosis Registry

Amyloidosis is a systemic disease resulting from the deposition of usually misfolded proteins in the form of amorphous fibrillar material in various tissues, potentially causing progressive dysfunction [1]. The prevalence of amyloidosis varies depending on the population and the type of amyloid. While the prevalence in the general population is unknown, estimates from the Mayo Clinic suggest it is 1 in 90,666% in the US [2]. In England, it generated approximately 0.0084% (1367/16232579) of the total hospital consultations between April 2008 and April 2009[3].

The most frequent clinical manifestations are cardiac, renal, and hepatic involvement, but these vary widely depending on the type of amyloidosis, the affected organ, and the extent of the deposits [4]. Amyloid infiltration can produce signs and symptoms that may be very similar to other rheumatological pathologies [5]. This potentially polymorphic clinical presentation may suggest underdiagnosis due to low clinical suspicion.

Records are organized systems for the systematic collection of data from a large number of patients in a fast and efficient manner, about a particular disease, at a given time [6, .].

The main difficulty with registries is ensuring the quality of their data. The main objectives of registries are [7]:

1. Understand the risk and prognostic factors of the disease.
2. Evaluate the diagnostic and therapeutic management by comparing it with current standards.
3. To advance knowledge of diseases in order to optimize the assessment, treatment and follow-up of patients.
4. Analyze the effectiveness of new therapies.
5. Study the differences between different populations.
6. Quickly estimate morbidity, mortality, and resource utilization associated with a pathological entity.
7. Examine the course of a disease
8. Formulate novel hypotheses for the subsequent performance of prospective studies.

Currently, there are registries for patients diagnosed with transthyretin amyloidosis (TAHOS) [8], and a global transplant registry for patients with familial amyloid polyneuropathy [9]. There are also indirect registries such as those for kidney transplantation, heart transplantation, and others [10].

We found no data on the prevalence, incidence, progression, or prognosis of amyloidosis in our country. There are also no current amyloidosis registries.

national or Latin American studies that could describe the behavior of this disease in our setting are essential. Because it is a chronic disease with amyloid infiltration and can produce signs and symptoms that are very similar to other rheumatological pathologies [5, 11], this potentially polymorphic clinical presentation may suggest underdiagnosis due to low clinical suspicion. Furthermore, there is no curative treatment, and some patients experience persistent symptoms despite appropriate therapy [12, 13]. Therefore, the creation of [a research group/research group/research group] is fundamental.

A monitoring system that generates data on disease progression and prognosis. Data from these registries can be used to develop new treatment guidelines and recommendations, and to inform and educate physicians on the management of this disease.

Because the Italian Hospital of Buenos Aires is a high-complexity referral center for this type of pathology and given that the hospital's prepaid health plan provides a unique opportunity for denominators to generate a population registry of its

members, we propose to create an Institutional Amyloidosis Registry.

## **Goals**

### **Primary objectives**

Creation of a system of **Population Registry of Amyloidosis** with prospective survey of epidemiological data, risk factors, diagnosis, prognosis, treatment, follow-up and survival.

### **Secondary objectives**

1. Describe the occurrence of **Amyloidosis** in the population of HIBA in the Central Hospital.
2. Describe the characteristics of the clinical presentation, evolution, and predisposing factors of **Amyloidosis**.
3. Describe epidemiological data through registry participation Latin American Amyloidosis Association.

### **Population and methods.**

#### **Design**

Multicenter Cohort Study

## **Scope**

The scope consists of the sectors of each senior citizens' hospital 17 years with amyloidosis from the participating centers.

The scope of the registry is the Italian Hospital of Buenos Aires. The registry will be institutional in nature, without excluding any area within the hospital setting, including the outpatient area (outpatient clinics, emergency room, demand and hospitalization in all areas of the central hospital).

In a second stage, other centers will be incorporated according to a preliminary feasibility assessment and a training program designed to train the different components.

## ***Eligible population***

All patients over 18 years of age and from any health provider who have amyloidosis or are suspected of having it will be included.

## **Selection criteria**

### **Inclusion Criteria**

Patients over 18 years of age with:

#### **Confirmed amyloidosis**

Demonstration of amyloid deposition by Pathological Anatomy in abdominal fat, bone marrow, rectum or involved organ (e.g., kidney, liver, sural nerve)

#### **Clinical case compatible with Amyloidosis but not confirmed:**

Cardiac: The presence of 2 or more of these points:

Right and/or left heart failure

ECG: decreased QRS complex voltage

Echocardiogram: increased wall thickness with hyperechoic ventricular walls and increased interatrial septum thickness. No other clear cause of increased ventricular thickness (hypertension, valvular heart disease).

Cardiac MRI: increased diffuse subendocardial gadolinium uptake on late images.

Renal:

Renal involvement plus serum lambda free chains

Evidence of clonal proliferation of plasma cells. This includes serum/urinary monoclonal protein, plasma cells in bone marrow, abnormal serum light chain ratio, without evidence of amyloid deposition composed of light chain fragments by immunofluorescence or immunohistochemistry, both lambda and kappa

Blood relatives of patients with confirmed familial amyloidosis

who present with a clinical picture of polyneuropathy without an alternative cause and a confirmed mutation of the amyloidogenic protein gene

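### The cardiac suspected-case rule excludes other causes only for wall thickness, so three of its six qualifying pairs exclude none, and the analyses do not separate suspected from confirmed cases

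*Combined protocol and SAP*

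**What the plan says.** The Inclusion Criteria have two tiers. The first is amyloid deposition shown by pathology. The second is headed "Clinical case compatible with Amyloidosis but not confirmed", and its cardiac entry reads "Cardiac: The presence of 2 or more of these points". Four points follow:

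- "Right and/or left heart failure"
- "ECG: decreased QRS complex voltage"
- "Echocardiogram: increased wall thickness with hyperechoic ventricular walls and increased interatrial septum thickness", followed directly by "No other clear cause of increased ventricular thickness (hypertension, valvular heart disease"
- "Cardiac MRI: increased diffuse subendocardial gadolinium uptake on late images"

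No point is mandatory. In the same tier, the route for blood relatives of patients with familial disease admits those "who present with a clinical picture of polyneuropathy without an alternative cause" who also carry a confirmed mutation.

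The *Eligible population* section includes suspected as well as confirmed patients, and item 3 under *Designs* follows both as a cohort. *Exclusion criteria* lists only refusal. *Data analysis* plans annual incidence and prevalence, descriptions of demographics, symptoms, diagnosis and treatment, and logistic regression; the follow-up analysis is a Cox survival model. None of these is said to be run by diagnostic tier.

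**The concern.** Heart failure and low QRS voltage are not specific to amyloidosis, and the rule attaches no condition about cause to either. A patient in whom both have another known explanation meets two points and qualifies as a suspected case, without any imaging sign of infiltration.

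That matters because suspected cases join the same registry as confirmed ones. The secondary objectives are to describe the occurrence, presentation, evolution and predisposing factors of amyloidosis. If suspected and confirmed cases are analysed together, patients without the disease add to the incidence and prevalence numerators. They also shift the symptom and treatment frequencies and bring their own mortality into the survival model.

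**Working it through.** The plan gives no figure on this point, so there is none to reproduce. The check is an enumeration of the rule, followed by a search for any later step that would close the gap.

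**1. Which combinations carry a cause exclusion?** Call the points H (heart failure), E (ECG), U (echocardiogram) and M (MRI). Only U has an alternative-cause clause.

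| Pair | Contains U? | Any cause exclusion? |
|---|---|---|
| H + E | no | none |
| H + M | no | none |
| E + M | no | none |
| H + U | yes | wall thickness only |
| E + U | yes | wall thickness only |
| U + M | yes | wall thickness only |

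Three of six pairs carry none. Counting every combination of two or more points gives 6 + 4 + 1 = 11. Those without U are the three pairs above plus H + E + M, so 4 of 11. H + E is the only pair with no imaging point.

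**2. Can the clause block entry?** No. It can only withhold point U. A patient whose thickened walls are clearly explained by hypertension does not score U, but still qualifies through H + E if both are present.

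**3. Does the layout change this?** If the clause was a separate line in the source document, its own words still limit it to causes of ventricular thickness. It would not reach other causes of heart failure or low voltage. Counted as a point of its own, it would make the rule looser.

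**4. Does a later step close the gap?**

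- *Exclusion criteria*: refusal only; an established alternative diagnosis does not exclude.
- *Data capture and collection circuit*: the standardized evaluation is for patients who already meet the criteria, and no step to rule out another cause is described.
- *Data logging*, *Follow-up* and *Data quality and completeness*: missing or erroneous fields, annual calls and consistency checks; none reclassifies a suspected case later found not to have amyloidosis.
- *Data analysis* and the follow-up analysis: no stated split by tier.

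**5. What would pooling do to prevalence?** Let f be the share of registered cases that are not amyloidosis. If all registered cases are counted and none is missed, prevalence is multiplied by 1/(1 − f). The documents do not give f, so these values are illustrative only:

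| Assumed f | 1/(1 − f) |
|---|---|
| 10% | 1/0.90 = 1.11 |
| 30% | 1/0.70 = 1.43 |
| 50% | 1/0.50 = 2.00 |

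**The case against.** **A suspected tier is meant to be sensitive.** The introduction justifies the registry by underdiagnosis from low clinical suspicion, and the tier is labelled as unconfirmed. This stands: breadth at entry is a legitimate choice. It does harm only if the tiers are pooled, and the plan does not say that they are kept apart.

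**Physicians will use judgement.** The capture system looks for suspected or confirmed amyloidosis, and the coordinator assigns each assessment to a physician, so not every patient with heart failure need be checked against the points. This also stands, and it is why the number of non-cases is unknown. But no text makes such judgement a condition of entry, and unwritten judgement is likely to vary once other centers join.

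**The plan has no general alternative-cause standard.** The renal and plasma-cell routes lack such a clause too, so the cardiac route does not breach a rule applied elsewhere. The familial route shows only that the authors used this condition in one place.

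**Stronger readings that the documents do not support.** A reader might infer that most patients entering by heart failure plus low voltage would not have amyloidosis. Figures can be produced for this. Assume amyloidosis in 1% to 5% of heart-failure patients, and low voltage in 50% of those with it and 5% to 10% of those without. The share with amyloidosis among entrants by this pair then runs from 0.01 × 0.5 / (0.01 × 0.5 + 0.99 × 0.10) = 0.005/0.104 = 4.8% to 0.05 × 0.5 / (0.05 × 0.5 + 0.95 × 0.05) = 0.025/0.0725 = 34.5%. The non-cases are then 95.2% to 65.5%. None of these inputs is in the documents, the 50% is held fixed, and the denominator is unselected heart failure rather than patients flagged on suspicion. The range cannot carry a conclusion.

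A reader might also infer that the registry could no longer describe amyloidosis. That does not follow, because pathology-confirmed cases can be described on their own.

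**Conclusion.** The gap in the wording is real. As written, the cardiac route admits patients by three of six pairs with no exclusion of another cause, and by one of those pairs with no imaging sign. Nothing later in the plan removes such patients or keeps them out of the incidence, prevalence, descriptive and survival results.

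This rests on a literal reading of the criteria and on the absence of any stated split by tier. The size of the effect cannot be determined: the documents give neither the number of patients who would enter by these pairs nor the share without amyloidosis. The CRF is not among the documents and may already record the points met. The matter should be settled before the first pooled report, but it does not undermine the description of confirmed cases.

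**What to change.** 1. State an alternative-cause condition for the whole cardiac entry, as the familial route does for polyneuropathy. The exact wording, including how coexisting hypertension or valve disease is handled, is for the sponsor's clinicians.
2. Record on the CRF which of the four points each patient met, so that those already registered can be reclassified. Without this, reclassification would need chart review.
3. In *Data analysis* and the follow-up analysis, report incidence and prevalence, case descriptions and survival for confirmed cases separately from suspected cases. This also covers the renal and plasma-cell routes.

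Do not make an echocardiogram or MRI point mandatory for entry. Patients who die or leave care before imaging would never be registered. That conflicts with the consecutive capture planned under *Designs* and could bias the survival analysis toward those who live long enough to be imaged.

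**Cost:** protocol wording, a few CRF fields and an extra split in the tables. Some suspected patients with a coexisting cardiac cause would not enter by the cardiac route; they could still enter if pathology confirms amyloid or if they meet another route. No test is added.

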## **Designs**

1. Prospective registration, with capture of consecutive cases and annual follow-up.
2. Cross-sectional descriptive studies for prevalence studies.
3. Follow-up cohort of patients with Amyloidosis or suspected Amyloidosis.
4. Retrospective cohort in the Latin American Amyloidosis Registry.5.

Data quality assessment and record validation.

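### As written, evidence of a plasma-cell clone is enough to register an unconfirmed case: the item asks for no organ finding, so gammopathy or myeloma without shown amyloid can enter the pooled analyses

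*Combined protocol and SAP*

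**What the plan says.** The combined protocol and SAP has two inclusion categories. The first, Confirmed amyloidosis, requires tissue proof: "Demonstration of amyloid deposition by Pathological Anatomy in abdominal fat, bone marrow, rectum or involved organ". The second is headed "Clinical case compatible with Amyloidosis but not confirmed" and lists several routes:

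- Cardiac: "Cardiac: The presence of 2 or more of these points", followed by heart failure, ECG, echocardiogram and MRI findings.
- Renal: "Renal involvement plus serum lambda free chains".
- Clone: "Evidence of clonal proliferation of plasma cells. This includes serum/urinary monoclonal protein, plasma cells in bone marrow, abnormal serum light chain ratio", qualified by "without evidence of amyloid deposition composed of light chain fragments by immunofluorescence or immunohistochemistry, both lambda and kappa".
- Familial: blood relatives of confirmed familial cases "who present with a clinical picture of polyneuropathy without an alternative cause and a confirmed mutation of the amyloidogenic protein gene".

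The Exclusion criteria section lists refusal only. The Designs section plans a "Follow-up cohort of patients with Amyloidosis or suspected Amyloidosis". The Data analysis section plans incidence and prevalence, case descriptions (demographics, symptoms, diagnostic methods, therapies and complications) and logistic regression. A Cox survival analysis follows on the tracking data. None of these is stated to be limited to confirmed cases.

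**The concern.** The markers in the clone item show that a plasma-cell clone exists. They do not show amyloid or an organ affected by it. If the item stands alone, the unconfirmed group can take in patients whose only relevant diagnosis is another plasma-cell disorder.

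Their symptoms, diagnostic methods, treatments, complications and survival would then be reported under the label of amyloidosis. This bears directly on the second secondary objective, which is to describe presentation, course and predisposing factors. It also bears on the first, occurrence, if unconfirmed cases are counted there; the plan does not say whether they are.

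**Working it through.** No arithmetic applies. The plan states no figure on this point, so the check is a reading of the eligibility logic.

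**1. What each unconfirmed route requires.**

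- Cardiac: at least two findings, all of them organ findings. The echocardiographic part also calls for no other clear cause of the wall thickening.
- Renal: organ involvement joined by an explicit *plus* to a light-chain finding. It does not mention alternative causes.
- Familial: polyneuropathy with no alternative cause, together with a confirmed mutation.
- Clone: evidence of clonal plasma-cell proliferation, with light-chain amyloid not shown. It names no organ finding, no symptom and no absence of another cause. It also does not say whether one of the listed markers suffices.

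The clone route is the only one of the four without a clinical picture.

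**2. What the negative clause does.** It requires that light-chain amyloid has not been demonstrated. A negative stain meets it, and on its wording so does the absence of a biopsy. It is slightly narrower than no amyloid of any kind, but any tissue-proven amyloid falls under the confirmed category. Someone who enters by this route alone therefore has no demonstrated amyloid.

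**3. Whether a later step removes such a patient.**

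- Exclusion criteria: refusal only. Gammopathy, myeloma and alternative diagnoses are not mentioned.
- Eligible population: admits suspected cases, but what counts as suspected is spelled out only in the list above.
- Data capture and collection circuit: the coordinator assigns watch-list patients to physicians, and anyone who meets the inclusion criteria and no exclusion criterion is evaluated and has the forms completed. No step is described for rejecting someone who meets the criteria.

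**4. Two test patients.** One has a monoclonal protein and no organ finding. The other has myeloma and a negative tissue stain. Both meet the words of the clone item, and neither is excluded. Both would be followed in the cohort and counted in the case descriptions and the Cox model.

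**5. Size.** The share of such entrants depends on how often clones are found in the source population and how many true suspected cases there are. The documents give neither, so no proportion or ratio follows from them.

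**The case against.** The strongest objection concerns layout. The clone item follows the Renal label, and the text was extracted from PDF: the familial item is split in mid-sentence, so indentation or bullets may be lost. The clone line could have been meant as a renal sub-point. This stands as doubt about intent. The wording points the other way, though. The renal line already has its own *plus*, and no connector joins it to the clone line. The renal line names lambda only, while the clone item covers lambda and kappa. The familial item, which is plainly not renal, sits under the same label.

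Second, the heading speaks of a clinical case, entry requires suspicion, physicians assess the watch list, and the reference to immunostaining suggests that tissue work-up was envisaged. This makes an incidental, asymptomatic entrant less likely. It does not close the gap, because neither the heading nor suspicion is defined apart from the list.

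Third, broad capture is defensible in a registry motivated by underdiagnosis, and the two categories can be separated. That is fair, but the plan does not commit to separating them, and separation alone would leave the unconfirmed group mixed.

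A reader might also infer that normal marrow would qualify, because the marrow marker has no percentage. It would not: that marker is an example under the requirement of clonal proliferation, so clonality is already demanded.

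**Conclusion.** The point holds as a gap in the eligibility wording. As written, a patient with a plasma-cell clone, no organ finding and no shown amyloid can be registered as a compatible case and carried into the pooled cohort, the case descriptions and the survival analysis. This rests on reading the clone item as a separate route, which the wording favours but the layout leaves open. If organ involvement was intended, the text still needs to say so.

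A reader might go further and infer that the suspected cohort would consist mainly of gammopathy and myeloma, or attach a ratio of such entrants to true cases. The documents do not support this. A ratio would need outside figures for clone frequency and testing. It would also have to set them against a general-population prevalence quoted for another country, while the hospital describes itself as a referral centre for this disease. The size is unknown, and the direction of any bias in the survival results cannot be derived either. The change should be made because the route to misclassification is open and closing it is cheap, not because a large effect has been shown.

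**What to change.** 1. Amend the clone item to require evidence of a plasma-cell clone **plus** at least one compatible organ finding (cardiac, renal, hepatic or polyneuropathy) without another clear cause. This follows the pattern of the plan's own renal line. Set the item apart from the Renal label, and say whether one of the listed clone markers is enough.
2. State in the Data analysis section that confirmed and unconfirmed cases are analysed separately in the occurrence, descriptive and survival analyses.

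The cost is a short amendment using data already in the record, and a split in the planned tables and models. The downside is that some early light-chain cases will be registered only once an organ finding or positive tissue appears. If the sponsor wants to keep clone-only patients in view until then, that needs its own provision: the watch list is described as a list of potentially eligible patients awaiting assessment, not as long-term surveillance of people who do not yet qualify.

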## **Exclusion criteria**

1. Refusal to participate in the study or the informed consent process by the patient or legal representative or refusal to consent to participate in the study in the case of minors.

